# **PROTOCOL SYNOPSIS**

| -  | ive, Pre-Market, Multicenter, Non-significant Risk Study to
Performance of the Poseidon™ System for Fluid Management
During Water-aided Colonoscopy.   |
|--|--|
| Study Design                                     | A prospective, pre-market, non-significant risk, multicenter trial   |
| Study
Objective                               | To validate the performance of the Poseidon System TM for fluid management during water-aided endoscopic procedures in the colon.   |
| Study Device
and Indication                   | The Poseidon TM System (WAE Design, LLC Northbridge, MA USA) consists of the following components:  |
| for Use  | • Poseidon Device (100001) (Single-use)  |
|  | • Waste bags Poseidon Device (100006) (Single-use)   |
|  | The Poseidon System is investigationally indicated to provide a pathway to control waste fluid during irrigation of the colon.   |
| Planned  | Up to 30 subjects  |
| Number of
Subjects                            | Fifteen subjects will be enrolled in this study and undergo water-aided colonoscopy with the Poseidon System. If the Primary Endpoint and Secondary Endpoint 1 are achieved in the first 15 subjects, the study will be complete.                    |
|  | If the Primary Endpoint or Secondary Endpoint 1 are not achieved,
changes to the device design will be made and this protocol will be
conducted again in a second group of 15 subjects with updated device.                                    |
| Planned
Number of
Investigational
Sites | 1-2 sites in the United States (US)  |
| Primary
Endpoint                              | 1. The design of the Poseidon System meets all acceptance criteria for design validation.  |
|  | a. User is able to operate device per the instructions for use.
This criterion will be assessed in a pass/fail manner with an
allowance of only 1 failure in the first 15 subjects and 1
failure in the second 15 subjects (if applicable). |

| -                      | ective, Pre-Market, Multicenter, Non-significant Risk Study to
e Performance of the Poseidon™ System for Fluid Management
During Water-aided Colonoscopy.  |
|------------------------|--|
|                        | 
 
b. User shall not adversely influence typical actuation of a scope
during colonoscopy procedure as assessed using a 5-point
Likert scale.
 
  |
|                        | c. User assessment of functional acceptability of Poseidon device ratchet location as assessed using a 5-point Likert scale.   |
|                        | d. User assessment of functional acceptability of Poseidon device intergluteal cleft fit as assessed using a 5-point Likert scale  |
|                        | e. The Poseidon System shall minimize passage of fluids
through and around the scope lumen when a scope is in the
device, as assessed using a 5-point Likert scale.  |
|                        | NOTE: Criteria B – E must have a mean Likert score of $>3$ to pass.   |
| Secondary
Endpoints | 1. Safety defined as the occurrence of all adverse events measured from the Index Procedure through the 2 Week Post Procedure Follow-up Visit.   |
|                        | 
 
a. The occurrence of > 2 device-related serious adverse events (SAE) is considered a failure 15 subjects and 1 failure in the second 15 subjects (if applicable).
 
   |
|                        | 2. Procedure time measured in minutes from the point of scope insertion to the point of scope removal (scope-in / scope-out).  |
|                        | 3. Device deficiencies defined as an inadequacy of a medical device
with respect to its identity, quality, durability, reliability, safety or
performance including malfunctions, use errors, and inadequate
labelling. |
| Follow-up              | Screening Visit  |
| Schedule               | a. Informed consent process  |
|                        | b. Selection criteria  |
|                        | 
 
Index Procedure Visit (May be Combined with Screening) (≤10 Days
of Index Procedure)
 
   |
|                        | a. Demographic information:  |

| - | ve, Pre-Market, Multicenter, Non-significant Risk Study to
erformance of the Poseidon™ System for Fluid Management
During Water-aided Colonoscopy. |
|---|--|
|   | i. Age at time of visit (years)  |
|   | ii. Gender   |
|   | iii. Height (cm)   |
|   | iv. Weight (kg)  |
|   | v. Race  |
|   | vi. Ethnicity  |
|   | b. Device information  |
|   | i. Device lot number   |
|   | c. Type of anesthesia  |
|   | i. MAC   |
|   | ii. General anesthesia   |
|   | d. Scope-in time (24-hour clock)   |
|   | e. Acceptance criteria for design validation   |
|   | f. Scope-out time (24-hour clock)  |
|   | g. Adverse events  |
|   | h. Device deficiencies   |
| • | Immediate Post Procedure Assessment  |
|   | a. Adverse events  |
| • | Discharge  |
|   | a. Date of discharge   |
| • | Unscheduled Visit  |
|   | a. Date of Unscheduled Visit   |
|   | b. Reason for Unscheduled Visit  |
|   | c. Adverse events  |
| • | 2 Week Post Procedure Follow-up (-3/+3 Days) (Telephone or Hospital)   |
|   | a. Adverse events  |
| • | End of Study   |

| A Prospective, Pre-Market, Multicenter, Non-significant Risk Study to
Validate the Performance of the Poseidon ™ System for Fluid Management
During Water-aided Colonoscopy. |  |  |
|---|--|--|
|   | a. End of study is defined as the completion of the 2-Week Post
Procedure Follow-up Visit, withdrawal or lost-to-follow-up.   |  |
| Study
Duration   | Each subject will participate in this study for approximately 2 weeks.
Enrollment of 30 subjects is anticipated to 2 months. Following
enrollment of the final subject the follow-up period will last
approximately 2 weeks. The entire study is anticipated to last a total of
3 months.  |  |
| Key Inclusion
Criteria   | 
 
Patients 18 years of age or greater.
 
Patients that have an indication to undergo water-aided colonoscopy.
 
Subjects with the ability to understand the requirements of the study, who have provided written informed consent, and who are willing and able to return for the required follow-up assessments.
 
  |  |
| Key Exclusion
Criteria   | 
 
Subject unable or unwilling to provide informed consent.
 
Subjects with prolapsing hemorrhoids that require intervention or
hemorrhoids that have been treated within last 3 months.
 
Prior TAMIS (Trans-anal minimally invasive surgery) or TEMS
(Trans-anal micro endoscopic surgery).
 
Any condition that in the opinion of the Investigator would create an
unsafe clinical situation that would not allow the patient to safely
undergo an endoscopic procedure.
 
Pregnant or lactating women or women of childbearing potential who
do not employ a reliable method of contraception as judged by the
Investigator, and/or are not willing to use reliable contraception for
the duration of study participation.
 
Patient is enrolled in another trial that could interfere with the
endpoint analyses of this trial.
 
 |  |
| Statistical
Methods  | This study is not powered and is being conducted by WAE Medical to
validate certain aspects of the Poseidon System design that are not
assessable in a bench or animal model.
Descriptive statistics will be used to analyze the Primary and Secondary
Endpoints. Data will be presented using means and standard deviations,
median, quartiles, and minimum and maximum, as applicable.  |  |

| _  | ctive, Pre-Market, Multicenter, Non-significant Risk Study to
Performance of the Poseidon ™ System for Fluid Management
During Water-aided Colonoscopy.   |
|--|--|
|  | Distributions of each continuous variable will be assessed prior to
analysis and examined for normality. Data with interval or ratio scales to
be analyzed that are not normally distributed will be analyzed using non-
parametric statistics.   |
| Primary
Analysis and
Passing
Validation | Primary Analysis:         The Primary Endpoint for this study is the assessment that the         Poseidon™ System meets all acceptance criteria for design validation.         a.       User is able to operate device per the instructions for use.         This criterion will be assessed in a pass/fail manner with an allowance of only 1 failure in the first 15 subjects and 1 failure in the second 15 subjects (if applicable). |
|  | 
 
b. User shall not adversely influence typical actuation of a scope
during colonoscopy procedure as assessed using a 5-point
Likert scale.
 
  |
|  | c. User assessment of functional acceptability of Poseidon device ratchet location as assessed using a 5-point Likert scale.   |
|  | d. User assessment of functional acceptability of Poseidon device intergluteal cleft fit as assessed using a 5-point Likert scale  |
|  | e. The Poseidon System shall minimize passage of fluids through and around the scope lumen when a scope is in the device, as assessed using a 5-point Likert scale.  |
|  | To assess whether the Primary Endpoint is met in each group of 15
subjects (as applicable), Criteria A-E must all pass receive a passing
score. The questionnaire attached in Appendix A will be answer during
each case to document performance of the Poseidon System relative to
Criteria A-E   |
|  | As defined above, criterion A will be assessed on a pass/fail basis. Only 1 failure in each group of 15 will be allowed; >1 failure will result in failure of criterion A.   |
|  | Criteria B – E will be assessed using a Likert-scale. After 15 each criterion has been assessed in all subjects, scores will be compiled by calculating a mean Likert-score. To pass, each criterion must have a   |

| -                    | ctive, Pre-Market, Multicenter, Non-significant Risk Study to
e Performance of the Poseidon™ System for Fluid Management
During Water-aided Colonoscopy.   |
|----------------------|--|
|                      | mean Likert score of >3. A score $\leq$ 3 is considered a failure. The rating of the Likert scale will be as follows:  |
|                      | • A value of 1 = Strongly Disagree   |
|                      | • A value of 2 = Disagree  |
|                      | • A value of 3 = Neutral   |
|                      | • A value of 4 = Agree   |
|                      | • A value of 5 = Strongly Agree  |
|                      | Passing Validation:  |
|                      | To pass overall validation in the first 15 subjects, the Primary Endpoint
and Secondary Endpoint 1 must receive passing scores. If this is
achieved in the first 15 subjects the Poseidon System has passed
validation and the study is considered complete. If this is not achieved,
design changes to the device are warranted.                                |
|                      | Once the design changes are made, the new device will be tested in an additional 15 subjects. The Primary Endpoint and Secondary Endpoint 1 must receive passing scores. If this is achieved in the second 15 subjects, the Poseidon System has passed the validation. If this is not achieved in the second group of 15 subjects the Poseidon System has failed validation. |
| Regulatory
Status | The Poseidon System is a pre-market investigational device that does not have regulatory clearance in the United States.   |

# 1. Introduction

Colonoscopy for the management of colorectal polyps is the standard of care in the United States with over 15-million procedures performed annually. For polyps greater than 10 mm, endoscopic mucosal resection (EMR) is performed to remove the tissue in a piece-meal fashion. Although effective, EMR presents challenges when perfomed during conventional colonoscopy such as high rates of polyp recurrance and low en-bloc resection, especially in polyps greater than 20mm.

The emergence of water-aided, or "underwater", colonoscopy to combat the challenges experiened during EMR with conventional procedures was first described by Binmoeller et al in 2012. During the procedure, the colon is filled with distilled water or a saline solution instead of air or carbon dioxide, which decreases tension in the colon wall and allows for a natural separation of the mucosal and submucosa from the muscularis propria. Light from the endoscope is refracted in the water which enhances magnification and visualization of tissue. Furthermore, the water or saline solution facilitates maneuverability of the endoscope and causes sessile or flat mucosal lesions to become more contracted and polypoid. All of this combined allows for improved yields during EMR resulting in higher rates of en bloc resection. A recent meta-analysis including 11 studies concluded that underwater EMR outperformed EMR during conventional colonoscopy for en-bloc resection and reported similar rates of intra-procedural and delayed bleeding.

Despite this evidence, there is low adoption of water-aided colonoscopy in everyday practice. A common reason for this is the management of fluid within the colon. There is no standard way to retain, exchange, or collect fluid during the procedure which inevitably results in excess fluid and bio waste leaking from the colon and collecting on the stretcher bed, under and around the patient.

The Poseidon™ System developed by WAE Medical to address the fluid management issues experienced during water-aided colonoscopy. The Poseidon device is inserted into the anal canal before the endoscope. A ratchet mechanism allows for adjustment of the introducer length due to variation in patient anatomy. Once the intruducer is secure a balloon is inflated to prevent fluid from passing out of the patient during a water aided endoscopy. Valves within the device faciliate controlled fluid drainage into an attached waste bag. The endoscope is then inserted into the Poseidon device to begin the colonoscopy. The aim of this study is to validate performance of the Poseidon System™ for fluid management during water-aided endoscopic procedures in the colon. .

# 2. Device Description

The Poseidon System is a fluid management system that is investigationally indicated to provide a pathway to control waste fluid during irrigation of the colon. The Poseidon device is a manually placed and controlled device that provides support and sealing on the perimeter of an endoscope while managing fluids naturally exiting the anus, during a colonoscopy procedure. The device consists of a introducer and hand piece that allows for passage of an endoscope with valves and a retention balloon that minimize fluid passage with a single-use

[figure not shown]

waste bag for collecting fluid and debris. The PoseidonTM System is not yet FDA 510(k) cleared.

#### 2.1. Device Components

The Poseidon System is comprised of the following components:

- **Poseidon Device (100001) (Single-Use):** The device consists of the introducer and balloon cuff insufflator. Once the introducer is lubricated on the balloon it is then inserted into the rectum and locked into place. The balloon is then inflated to stabilize the device before the endoscope is inserted. (Figure 1)
- **Poseidon Waste bag (Single-use):** The waste bag is attached to the vacuum line outside the subject allowing for fluid to be drained into the bag. It is regulated with a relief valve. (**Figure 2**)

#### Figure 1: Poseidon Device:

#### 2.2. Pre-clinical Testing

The following is a list of completed testing to support a future the IRB submission and possible 510(k):

- Sterility: Validation results are not required for the submission. Sterilization method is hydrogen peroxide (H2O2)
- Shelf Life: Including device performance, package integrity testing after simulated distribution and accelerated aging to support an expiration date. Shelf life is 6 months.
- Biocompatibility: Testing per 10993-1 for all patient contacting materials

Figure 2: Poseidon Waste Bag:

- Verification: Testing as determined by Risk Management and design requirements including includes tensile, dimensional, stiffness or other testing of product attributes
- Simulated use: In a bench top model demonstrating intended user can use the device as intended and device performs to specification.

# 3. Study Objectives

To validate the performance of the PoseidonTM System for fluid management during wateraided endoscopic procedures in the colon.

# 4. Study Endpoints

#### 4.1. Primary Endpoint

The primary endpoint for this study is the assessment that the Poseidon device meets all acceptance criteria for design validation.

- 1. The design of the Poseidon System meets all acceptance criteria for design validation.
  - a. User is able to operate device per the instructions for use. This criterion will be assessed in a pass/fail manner with an allowance of only 1 failure in the first 15 subjects and 1 failure in the second 15 subjects (if applicable).
  - b. User shall not adversely influence typical actuation of a scope during colonoscopy procedure as assessed using a 5-point Likert scale.
  - c. User assessment of functional acceptability of Poseidon device ratchet location as assessed using a 5-point Likert scale.
  - d. User assessment of functional acceptability of Poseidon device intergluteal cleft fit as assessed using a 5-point Likert scale
  - e. The Poseidon System shall minimize passage of fluids through and around the scope lumen when a scope is in the device, as assessed using a 5-point Likert scale.

**NOTE:** Criteria B – E must have a mean Likert score of >3 to pass. The rating of the Likert scale will be as follows:

- A value of 1 = Strongly Disagree
- A value of 2 = Disagree
- A value of 3 = Neutral
- A value of 4 = Agree
- A value of 5 = Strongly Agree

The questionnaire that will be used to assess the Primary Endpoint is attached in Appendix A.

# 5. Study Design

This study is a prospective, pre-market, non-significant risk, multicenter trial.

#### 5.1. Scale and Duration

Up to 30 subjects will be enrolled in this study.

Initially 15 subjects will be enrolled in this study and undergo water-aided colonoscopy with the Poseidon™ System. If the Primary Endpoint and Secondary Endpoint 1 are achieved in the first 15 subjects, the study will be complete.

If the Primary Endpoint or Secondary Endpoint 1 are not achieved, changes to the device design will be made and this protocol will be conducted again in a second group of 15 subjects with updated device. All studies sites and associated IRBs will be notified if the second group of 15 subjects will need to be enrolled.

It is anticipated that enrollment of the first 15 subject will take a period of 2 month. If enrollment of the second 15 subjects is required, it is estimated that device design changes will take 1-2 months, and enrollment of the second group of 15 subjects will take a period of 2 months.

Each subject will be followed for approximately 2 weeks following the procedure. Overall the study take 3-7 months to complete.

#### 5.2. Study Devices

All subjects enrolled in this study will undergo water-aided colonoscopy with fluid management performed by the PoseidonTM System. All devices used during the procedure be captured on the applicable case report form (CRF).

#### 5.3. Non-significant Risk Justification

Per 21 CFR 812.3, a significant risk device means an investigational device that:

- Is intended as an implant and presents a potential for serious risk to the health, safety, or welfare of a subject;
- Is purported or represented to be for use supporting or sustaining human life and presents a potential for serious risk to the health, safety, or welfare of a subject;
- Is for a use of substantial importance in diagnosing, curing, mitigating, or treating disease, or otherwise preventing impairment of human health and presents a potential for serious risk to the health, safety, or welfare of a subject; or
- Otherwise presents a potential for serious risk to the health, safety, or welfare of a subject.

The Poseidon System does not meet any of the above criteria of a significant risk device and therefore can be categorized as a non-significant risk (NSR) device.

#### 5.4. Justification for Study Design

WAE Medical is conducting this NSR study to validate certain aspects of the Poseidon System design that are not assessable in a bench or animal model. The study will be conducted according to abbreviated IDE regulations as per 21 CFR 812.2(b) and will require the approval of NSR status by all participating IRBs.

## 6. Subject Selection

Patients who meet all of the inclusion criteria and none of the exclusion criteria will be considered for enrollment in this study.

#### 6.1. Inclusion Criteria

- 1. Patients 18 years of age or greater.
- 2. Patients that have an indication to undergo water-aided colonoscopy.
- 3. Subjects with the ability to understand the requirements of the study, who have provided written informed consent, and who are willing and able to return for the required follow-up assessments.

#### 6.2. Exclusion Criteria

- 1. Subject unable or unwilling to provide informed consent.
- 2. Subjects with prolapsing hemorrhoids that require intervention or hemorrhoids that have been treated within last 3 months.
- 3. Prior TAMIS (Trans anal minimally invasive surgery) or TEMS (Trans anal micro endoscopic surgery).
- 4. Any condition that in the opinion of the Investigator would create an unsafe clinical situation that would not allow the patient to safely undergo an endoscopic procedure.
- 5. Pregnant or lactating women or women of childbearing potential who do not employ a reliable method of contraception as judged by the Investigator, and/or are not willing to use reliable contraception for the duration of study participation.
- 6. Patient is enrolled in another trial that could interfere with the endpoint analyses of this trial.

## 7. Subject Accountability

#### 7.1. Point of Enrollment

Subjects may be enrolled in this study if they sign and date the informed consent form (ICF) and meet all of the selection criteria noted in Section 6 of this protocol. No study-related activity can take place until the subject is considered enrolled.

#### 7.2. Screen Failure

Patients that do not meet the selection criteria noted in Section 6 of this protocol will be considered Screen Failures. Subjects that are enrolled in the study may screen out of the study up to, and during the index procedure if any of the selection criteria noted in Section 6 of the protocol are found not to be met. Screen failures will not be counted towards enrollment and will be replaced. Screen failures will be accounted for on the applicable case report form (CRF).

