#### 7.3. Withdrawal

Study participation is voluntary and a subject may decide to withdraw their consent at any time with or without reason and without impact on their continued medical care.

A study Investigator may withdraw a subject form the study without the subject's consent. If this occurs, the Investigator will inform the subject. Reasons for subject withdrawal by an Investigator may include, but are not limited to:

- The Investigator decides it is in a subject's best interest not to continue participating in the study.
- The Investigator decides that it may be harmful for a subject to continue participating in the study.

- The subject is not compliant with study required follow-up.
- The study Sponsor (WAE Medical, Inc.) terminates the study early.
- The IRB, EC, or a regulatory agency decides to terminate the study early.
- The subject is considered lost-to-follow-up.

If a subject withdraws from the clinical study or if they are withdrawn by an Investigator, their status and reason for withdrawal will be documented on the applicable study CRF.

Subjects that withdraw or are withdrawn by the Investigator from the study after undergoing treatment with the study or control device will not be replaced for enrollment. Subjects who withdraw or are withdrawn from the study prior to undergoing treatment with the study or control device will be replaced for enrollment.

All applicable CRFs up to the point of withdrawal must be completed and will be used for analysis.

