#### 8.1. Data Collection Schedule

Table 1.0 below provides a schedule of required study visits as well as assessments. Details regarding each study visit are provided in the following sections.

| Procedure/Assessment                        | Screening*
(≤10 Days of Index
Procedure) | Index Procedure
(0 Days) | Discharge | Follow-up Visits       |                      |
|---|--|-----------------------------|-----------|------------------------|----------------------|
|   |  |                             |           | 2 Weeks×
(± 7 Days) | Unscheduled
Visit |
| Informed Consent                            | X  |                             |           |                        |                      |
| Inclusion / Exclusion                       | X  |                             |           |                        |                      |
| Enrollment                                  | X  |                             |           |                        |                      |
| Demographics                                |  | X                           |           |                        |                      |
| Medical History                             |  | X                           |           |                        |                      |
| Device Information                          |  | X                           |           |                        |                      |
| Anesthesia Information                      |  | X                           |           |                        |                      |
| Acceptance Criteria for Design Validation   |  | X                           |           |                        |                      |
| Total Procedure Time (Scope-in / Scope-out) |  | X                           |           |                        |                      |
| Adverse Events                              |  | X                           | Х         | Х                      | X                    |
| Device Deficiencies                         |  | X                           |           |                        |                      |
| End of Study §                              |  |                             |           | Х                      |                      |

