#### 8.3. Screening (Within 10 Days of Index Procedure) (Hospital/Clinic Visit)

The Screening Visit may be performed at the same time as the Index Procedure. During the Screening Visit the following data collection and assessments will be performed:

- 1. Date of visit
- 2. Informed consent process
- 3. Inclusion/Exclusion criteria (refer to Section 6 of this protocol)
- 4. Enrollment (refer to Section 7 of this protocol)

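### Section 7.2 puts no device-exposure cut-off on screen failure, so a subject already exposed to the device can be uncounted and replaced, which can turn criterion A from 2/15 (fail) into 1/15 (pass)

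*Combined protocol and SAP*

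**What the plan says.** Section 7.2 (Screen Failure) states that enrolled subjects "may screen out of the study up to, and during the index procedure if any of the selection criteria noted in Section 6" are found not to be met. It continues: "Screen failures will not be counted towards enrollment and will be replaced". Screen failures are logged on a case report form. Use of the device is not mentioned. Section 8.3.1 repeats, as consent wording, that a subject may screen out during the procedure.

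Section 1 gives the order of events: "The Poseidon device is inserted into the anal canal before the endoscope". Section 8.4.1 likewise has the system placed before colonoscopy starts.

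Section 7.3 (Withdrawal) does divide by exposure. Subjects withdrawn "after undergoing treatment with the study or control device will not be replaced for enrollment", while those withdrawn "prior to undergoing treatment with the study or control device will be replaced for enrollment". Sections 7.3 and 7.4 both add that forms completed up to withdrawal or loss to follow-up are used for analysis. Section 7.2 has no such sentence. The protocol does not define what counts as treatment.

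Sections 9.1.1 and 9.4 allow one criterion A failure per group of 15; more than one fails the criterion. Under Section 9.5 all of criteria A–E, together with Secondary Endpoint 1, must pass for the device to pass validation. Section 9 defines no analysis population.

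**The concern.** Whether a case counts should be settled before its outcome can be seen. Under Section 7.2 it can be settled afterwards, because the window for screen-out stays open through the index procedure and the device is placed early in it. Two subjects with the same device exposure can be handled in opposite ways: one labelled a withdrawal stays in the count, and one labelled a screen failure is replaced. An attempted but failed placement is the hardest case, since treatment in Section 7.3 is undefined.

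Most Section 6 criteria are facts of history or status, known beforehand. Two could plausibly come to light at insertion: exclusion 2 (prolapsing hemorrhoids) and exclusion 4 (a condition the investigator judges unsafe). That is my inference; the protocol does not say so. If it is right, removal need not be independent of a difficult placement. With a margin of one failure, a single case can decide criterion A and so the validation result.

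**Working it through.** **1. What the text allows.** Screen-out may occur during the index procedure (7.2). The device is placed before the scope (1, 8.4.1). Time after an attempted insertion is therefore not excluded. Same-day screening does not require this latitude. Section 8.3 says "The Screening Visit may be performed at the same time as the Index Procedure", but Section 7.1 makes enrollment conditional on meeting all selection criteria and adds "No study-related activity can take place until the subject is considered enrolled". The schedule in Section 8.1 marks "Inclusion / Exclusion" at Screening only.

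**2. What happens to the data.** Section 7.2 does not say outright that the data of an exposed screen failure leave the analysis. It is the natural reading, because the group is 15 counted subjects and 7.2 lacks the data-use sentence of 7.3 and 7.4.

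**3. The decision rule.** The plan gives no assumed rate, power or error level to reproduce; its only figure is the limit of one failure in 15.
- Both failing subjects kept: 2/15 = 13.3%, fail.
- One screened out and replaced by a success: 1/15 = 6.7%, pass.

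**4. Size.** Assume independent cases with true failure rate p. The documents give no value for p or for the share of failing cases screened out, so both are varied.

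Baseline, P(X ≤ 1) for X ~ Bin(15, p):
- p = 10%: 0.2059 + 0.3432 = 0.549
- p = 20%: 0.0352 + 0.1319 = 0.167
- p = 30%: 0.0047 + 0.0305 = 0.035

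If a share s of failing cases is screened out and replaced, the failure rate among counted subjects becomes q = p(1 − s)/(1 − ps). For p = 10% and s = 10%, q = 0.09/0.99 = 0.0909. P(pass) is then P(X ≤ 1) for X ~ Bin(15, q):

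| p | s = 0 | 1% | 2% | 5% | 10% |
|---|---|---|---|---|---|
| 10% | 54.9% | 55.4% | 55.9% | 57.3% | 59.8% |
| 20% | 16.7% | 17.1% | 17.5% | 18.7% | 20.8% |
| 30% | 3.5% | 3.7% | 3.8% | 4.2% | 5.1% |

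If 10% of cases are removed without regard to outcome, simulation gives 55.0% at p = 10% and 16.7% at p = 20%, which is no change beyond simulation error.

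**5. Extreme case.** Suppose one failing case is always removed when exactly two of 15 fail. P(pass) rises by P(X = 2) × (1 − p):
- p = 10%: 0.549 + 0.240 = 0.789
- p = 20%: 0.167 + 0.185 = 0.352
- p = 30%: 0.035 + 0.064 = 0.099

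Section 7.2 sets no cap on replacements. With two such removals, P(Bin(17, p) ≤ 3) is 91.7% at p = 10% and 54.9% at p = 20%.

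**The case against.** The best defence is that Sections 7.2 and 7.3 deal with different events, ineligibility and withdrawal, and that limiting a design validation to eligible subjects is a reasonable choice. Screen-out requires an unmet Section 6 criterion. Exclusion 4 concerns whether the patient can safely have an endoscopic procedure at all, so it is hard to invoke for device trouble when colonoscopy goes ahead. An investigator who stops in the subject's interest falls under 7.3. Screen failures are logged, and Section 12 requires deviations to be documented. The study is unpowered and descriptive.

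Much of this stands. It makes the route narrow and the expected effect small, and it means the two sections are differently framed rather than contradictory. It does not close the gap: a log entry makes a removal visible but does not put the case back in the count, and descriptive or not, the study ends in a pass/fail decision.

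Three stronger readings should be resisted. A reader might infer that investigators may discard device failures; Section 7.2 permits no such reason. A reader might take 78.9% as the likely effect or as the limit; it needs an unmet criterion in a failing case whenever exactly two fail, and it covers one removal only. A reader might also suppose that serious adverse events would be lost. Section 9.4 fails Secondary Endpoint 1 on more than two device-related events without a denominator, and Section 17.4 starts reporting at the index procedure, so the text leans towards counting them. Only the reference in Section 9.5 to the first 15 subjects leaves doubt.

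**Conclusion.** The point holds as a gap in the counting rule. Section 7.2 allows a device-exposed subject to be uncounted and replaced, and one such replacement can reverse criterion A. At assumed screen-out shares of 1% to 10% of failing cases, the gain in the chance of passing is about 0.5 to 4.9 percentage points at a 10% failure rate, 0.4 to 4.1 at 20% and 0.1 to 1.6 at 30%. These figures rest on independent cases and on rates the documents do not supply. The conclusion also rests on reading 7.2 as removing such subjects from the analysis, which is inferred. Nothing in the documents shows that the clause was written for this purpose. The change should be made because it is cheap and the margin is a single failure, not because a large bias is expected.

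**What to change.** State in Section 7.2, and align Section 8.3.1, that a subject may be screened out and replaced only before the first attempted insertion of the Poseidon device, defined as the introducer first being applied to the anal canal. Use the same cut-off in Section 7.3 in place of the undefined reference to treatment. Then state that:

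- every subject with an attempted insertion stays in the group of 15;
- criterion A is scored as observed;
- any device-related serious adverse event in such a subject counts toward Secondary Endpoint 1;
- ineligibility discovered later is reported as a protocol deviation.

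This concerns counting only and does not limit the investigator's freedom to stop using the device or to stop the procedure. No new averaging rule for criteria B–E is proposed: taking means only over rated subjects could itself lose the poor cases.

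The cost is wording in three sections and no extra subjects. The price is a possibly less favourable criterion A result and a few ineligible subjects kept in the count.
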